### 10.2.1 Grading and Relationship to Drug

The descriptions and grading scales found in the CTEP Version 4 of the NCI Common Terminology Criteria for Adverse Events (CTCAE) will be utilized for AE reporting. CTEP Version 4 of the CTCAE is identified and located at:

[http://ctep.cancer.gov/protocolDevelopment/electronic\\_applications/ctc.htm](http://ctep.cancer.gov/protocolDevelopment/electronic_applications/ctc.htm).

AEs not covered by specific terminology listed should be reported with common medical terminology, and documented according to the grading scales provided in the CTCAE Version 4.

The relationship of event to study drug will be documented by the Investigator as follows:

- **Unrelated:** The event is clearly related to other factors such as the participant's clinical state, other therapeutic interventions or concomitant drugs administered to the participant.
- **Unlikely:** The event is doubtfully related to investigational agent(s). The event was most likely related to other factors such as the participant's clinical state, other therapeutic interventions, or concomitant drugs.
- **Possible:** The event follows a reasonable temporal sequence from the time of drug administration, but could have been produced by other factors such as the participant's clinical state, other therapeutic interventions or concomitant drugs.
- **Probable:** The event follows a reasonable temporal sequence from the time of drug administration, and follows a known response pattern to the study drug. The event cannot be

reasonably explained by other factors such as the participant's clinical state, therapeutic interventions or concomitant drugs.

- **Definite:** The event follows a reasonable temporal sequence from the time of drug administration, follows a known response pattern to the study drug, cannot be reasonably explained by other factors such as the participant's condition, therapeutic interventions or concomitant drugs; AND occurs immediately following study drug administration, improves upon stopping the drug, or reappears on re-exposure.

### Boehringer Ingelheim Reporting Requirements

- The severity of the AE should be judged based on the following:
- The severity of adverse events should be classified and recorded in the eCRF according to the Common Terminology Criteria for Adverse Events (CTCAE) CTEP Version 4 of the NCI CTCAE located at:  
[http://ctep.cancer.gov/protocolDevelopment/electronic\\_applications/ctc.htm](http://ctep.cancer.gov/protocolDevelopment/electronic_applications/ctc.htm) Causal relationship of adverse event

Medical judgment should be used to determine the relationship, considering all relevant factors, including pattern of reaction, temporal relationship, de-challenge or re-challenge, confounding factors such as concomitant medication, concomitant diseases and relevant history. Assessment of causal relationship must be recorded for each adverse event.

Causality will be reported as either "Yes" or "No":

**Yes:** There is a reasonable causal relationship between the investigational product administered and the AE ("Yes" is equivalent to: Possible, Probable or, Definite).

**No:** There is no reasonable causal relationship between the investigational product administered and the AE ("No" is equivalent to Unrelated or Unlikely).

### 10.2.2 Reporting Adverse Events

**Table 15 Guidelines for Routine Adverse Event Reporting for Phase 1 Studies (Regardless of Expectedness)**

| Attribution | Grade 1 | Grade 2 | Grade 3 | Grade 4 |
|-------------|---------|---------|---------|---------|
| Unrelated   | X       | X       | X       | X       |
| Unlikely    | X       | X       | X       | X       |
| Possible    | X       | X       | X       | X       |
| Probable    | X       | X       | X       | X       |
| Definite    | X       | X       | X       | X       |

**Table 16 Guidelines for Routine Adverse Event Reporting Phase 2 Studies (Regardless of Expectedness)**

| Attribution | Grade 1 | Grade 2 | Grade 3 | Grade 4 |
|-------------|---------|---------|---------|---------|
| Unrelated   |         |         | X       | X       |
| Unlikely    |         |         | X       | X       |
| Possible    | X       | X       | X       | X       |
| Probable    | X       | X       | X       | X       |
| Definite    | X       | X       | X       | X       |

Routine AEs occurring from the date the participant signs the study consent until 30 days after the last intervention or until the event has resolved, the study participant is lost to follow-up, the start of a new treatment, or until the study investigator assesses the event(s) as stable or irreversible, will be reported. New information will be reported after it is received.

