| Statistical Analysis | 
Sample Size Determination: Sample size determination for the phase I portion will depend upon the dose-toxicity profile, but is expected to be between 9-18 patients. For the phase II portion, with an alpha of 0.1, assessment of 36 patients allows for a power of 0.8 to detect a minimum difference of 17% in the PFS at 18 weeks, assuming a rate of 25% under standard of care.
 
Randomization: No randomization is required.
 
Efficacy Analysis: Primary interest is in the PFS at 18 weeks after enrollment. The PFS at 18 weeks will be described by binomial proportion estimates and 90% confidence intervals. All patients in the phase II study and those treated at the RP2D in the phase I study will be included for analysis.
 
Safety Analysis: Adverse events will be tabulated. AE rates will be described using binomial proportions and 90% confidence intervals.
 
Correlative Data Analysis: Mechanistic PK/PD modeling will be employed, examining the relationship between nintedanib pharmacokinetics, modulation of CAFs and PFS.
 |
|-----------------------------|--|

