#### 4.2 Target Accrual and Study Duration

It is expected that a total of 9 patients will be enrolled at two dose levels in the Phase I portion, with potential for a maximum of 18 patients. The number of participants required is a function of the unknown dose-toxicity relationship. Patients treated at the RP2D (n=6) will be included in the Phase II study analysis. Up to an additional 30 patients will be enrolled in the Phase II portion of the study, for a Phase II sample size of 36. Summarily, the study is expected to accrue 39 patients (9 + 36 - 6). However, if toxicity is greater than expected, a maximum of 48 patients might be required (18 + 36 - 6). Enrollment is expected to be split between the two sites involved: Roswell Park Cancer Institute and City of Hope. Thus, in the case of 39 patients being enrolled, it is anticipated that approximately 20 patients would be enrolled at RPCI and 19 at City of Hope. Accrual is expected to take up to 2 years. Median PFS has historically stood at approximately 2 months and this study aims to provide a PFS rate at 18 weeks (~4 months) of 40%. It is anticipated that patients will be on study for approximately 18 weeks.

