## **10 SAFETY EVALUATION**

### **10.1 Adverse Events**

#### **10.1.1 Definition**

An adverse event or adverse experience (AE) is defined as any untoward medical occurrence (including an exacerbation of a pre-existing condition) associated with the use of a drug in humans, whether or not considered drug related (i.e., the event does not necessarily have to have a causal relationship with the treatment). Therefore, an AE can be ANY unfavorable and unintended sign (including an abnormal laboratory finding), symptom, or disease temporally associated with the use of a medicinal (investigational) product, whether or not considered related to the medicinal (investigational) product (attribution of ‘unrelated’, ‘unlikely’, ‘possible’, ‘probable’, or ‘definite’). In addition, each study site will also be responsible for reporting causality of AEs to Boehringer Ingelheim as per **Section 10.2.1**.

An AE is considered “unexpected” if it is not listed in the investigator brochure or is not listed at the specificity or severity that has been observed; or if an investigator brochure is not required or available, is not consistent with the risk information described in the general investigational plan in other study-related documents.

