**12 STATISTICAL METHODOLOGY**

This is a Phase I/II study. The Phase 1 is included to compensate for the current lack of toxicity information about nintedanib and capecitabine combination treatment. A standard 3+3 dose escalation design is considered, where a maximum of 18 patients are enrolled.

Phase II is a single arm – single stage study, where a total of n=36 (including 6 treated at the RP2D in Phase I) patients with refractory metastatic colorectal cancer will be enrolled and treated with a combination of nintedanib and capecitabine, as previously outlined. There is no formal interim analysis planned or early stopping rules. However, toxicity and safety outcomes will be regularly reviewed.

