### **12.4.1 Adverse Event**

The frequency of toxicities will be tabulated by grade across all dose levels and cycles. The frequency of toxicities will also be tabulated for the dose estimated to be the MTD. All participants who receive any study treatment will be considered evaluable for toxicity.

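### Phase II reporting omits grade 1-2 events judged unrelated or unlikely, Phase I reporting includes them, and the plan pools both phases into AE rates by grade

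*Combined protocol and SAP*

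**What the plan says.** Section 10.2.2 has one table per phase. Table 15, "Guidelines for Routine Adverse Event Reporting for Phase 1 Studies (Regardless of Expectedness", marks all four grades for all five attribution categories. Table 16, "Guidelines for Routine Adverse Event Reporting Phase 2 Studies (Regardless of Expectedness", marks all four grades for possible, probable and definite events, but only grades 3 and 4 for unrelated and unlikely events.

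The definition of an AE in Section 10.1.1 is all-cause: "whether or not considered drug related (i.e., the event does not necessarily have to have a causal relationship with the treatment".

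The analysis sections do not carry the difference forward. Section 12.4.1 says "The frequency of toxicities will be tabulated by grade across all dose levels and cycles", adds a tabulation at the dose estimated to be the MTD, and sets the denominator: "All participants who receive any study treatment will be considered evaluable for toxicity". The Synopsis says "AE rates will be described using binomial proportions and 90% confidence intervals". Section 12.3 (Secondary Analysis) covers both toxicities and adverse events, uses 90% Wilson intervals, and expects Phase II widths of about 0.17 to 0.26 for true rates of 0.10 to 0.50. Section 12 describes the Phase II set as "a total of n=36 (including 6 treated at the RP2D in Phase I" and lists aggregate AE rates among the secondary endpoints. No section splits AE rates by phase or attribution, or restricts them to related events.

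**The concern.** A low-grade event judged unrelated or unlikely can reach the tables from a Phase I patient but, on Table 16 as written, not from a patient enrolled in Phase II. The denominator counts both kinds of patient. An all-cause grade 1-2 rate built this way is too low, and its Wilson interval is centred on a quantity that is neither the all-cause rate nor the related-event rate.

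Toxicity is a stated secondary objective of Phase II. Attribution matters in this setting: Section 10.2.1 lets investigators assign events to the participant's clinical state, and in refractory metastatic disease without a control arm many low-grade symptoms could be placed there. At stake is the descriptive low-grade safety profile at the recommended Phase II dose (RP2D).

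**Working it through.** **Inputs.** Phase II analysis set 36, of whom 6 come from Phase I (Section 12). New Phase II patients: "Up to an additional 30 patients will be enrolled in the Phase II portion of the study" (Section 4.2). Interval: 90% Wilson, true rates 0.10 to 0.50, stated widths 0.17 to 0.26 (Section 12.3). RP2D already determined to be dose level 2 (Sections 4.1.2 and 6.2).

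**1. Which patients are in the planned rate?** Wilson width = 2z·sqrt[p(1-p)/n + z²/(4n²)] / (1 + z²/n), with z = 1.645.

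- n=36, p=0.10: 2(1.645)·sqrt(0.002500 + 0.000522)/1.0752 = 0.168
- n=36, p=0.50: 2(1.645)·sqrt(0.006944 + 0.000522)/1.0752 = 0.264

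These reproduce the stated 0.17 and 0.26. Other denominators do not match both ends: n=30 gives 0.185 and 0.288, n=39 gives 0.161 and 0.255, n=48 gives 0.145 and 0.231. The planned Phase II AE rate therefore combines 6 patients under Table 15 with 30 under Table 16.

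**2. How many patients have full capture?** In the RP2D set, 6 of 36 (17%). For the table across all dose levels, the Phase I count matters. Under Section 6.2 and Table 3, reaching dose level 2 as the RP2D means 3 or 6 patients at level 1 and 6 at level 2, with level -1 never opened. That gives 9 to 12 Phase I patients, barring replacements under Section 6.4. Full capture is then 9 of 39 (23%) to 12 of 42 (29%).

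**3. Bias.** Let p be the true proportion of patients with an all-cause grade 1-2 event of the kind being rated, and u the share of those patients whose only such events are unrelated or unlikely. With f fully captured patients among n:

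E[rate] = [f·p + (n-f)·p·(1-u)]/n, so relative bias = -((n-f)/n)·u.

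For the RP2D set this is -(30/36)u = -(5/6)u. The documents give no value for u, so a range is assumed:

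| Set | Fully captured | u=0.10 | u=0.25 | u=0.50 |
|---|---|---|---|---|
| Phase II enrolled only | 0 of 30 | -10% | -25% | -50% |
| RP2D set | 6 of 36 | -8% | -21% | -42% |
| All treated, 9 in Phase I | 9 of 39 | -8% | -19% | -38% |
| All treated, 12 in Phase I | 12 of 42 | -7% | -18% | -36% |

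**4. Against the plan's own precision at n=36.** At p=0.50 the half-width is 0.264/2 = 0.132. The expected estimate is 0.458, 0.396 or 0.292 for u = 0.10, 0.25 or 0.50, that is, shifts of 0.042, 0.104 and 0.208. The shift exceeds the half-width once u passes 0.132/(0.50 × 5/6) = 0.32. At p=0.10 the half-width is 0.168/2 = 0.084, and even u=0.50 shifts the estimate by only 0.10 × 0.417 = 0.042.

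**5. What is untouched.** Possible, probable and definite events of any grade, and all grade 3-4 events, are marked in both tables, so their bias from this source is zero.

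**The case against.** The strongest reply is that Tables 15 and 16 govern reporting, not recording. The CRF recording rules in Section 10.1.1 have no phase or attribution filter, Section 10.2.1 asks for a causality assessment of every AE, and Table 12 collects AEs on Day 1 of each Phase II cycle. If sites enter every AE and the analysis uses the full eCRF, the bias is zero. That possibility stands, and for that reason the point is conditional. It does not close the matter. Serious events and events of special interest have their own reporting rules (Sections 10.2, 10.3.2 and 10.4), so Section 10.2.2 is the only stated scope for routine AEs, and nothing says that the blank cells are collected anyway.

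A second reply is that toxicities means drug-related events, for which capture is the same in both phases. The term is undefined. Section 6.8 speaks of toxicity that may be related or unrelated, and the Synopsis and Sections 12 and 12.3 also promise AE rates.

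A reader might infer more than the documents support:

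- *That pooling causes the understatement.* Table 16 does. Phase II patients alone would lose the full u; adding 6 fully captured patients reduces this to (5/6)u. Pooling contributes the mixed denominator.
- *That low-grade rates fall to one sixth of the truth (6/36).* This is the case u=1, a rate of unrelated or unlikely events only, which the plan does not specify.
- *That up to 18 of 48 patients have full capture.* Those are the planning maxima; they cannot arise with dose level 2 already the RP2D, barring replacements.
- *That dose-level AE comparisons are distorted.* None is specified. The by-dose-level breakdown in Section 12.3 concerns tumour response.

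**Conclusion.** The point holds as a minor one. Taken as written, the plan gives all-cause grade 1-2 rates that are understated because of Table 16 and that mix two capture rules under one denominator. At n=36 the relative understatement is (5/6)u, or 8% to 42% over the assumed range of u from 0.10 to 0.50. The true size cannot be computed because u is not given.

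The conclusion rests on two readings that the documents leave open: that Table 16 limits what reaches the Phase II eCRF, and that the planned rates include all-cause events. If either is wrong, the problem reduces to a missing sentence. The effect is confined to a descriptive secondary endpoint. Related-event rates, grade 3-4 rates, dose-limiting toxicities and the test of 18-week PFS are unaffected.

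**What to change.** First establish whether the Phase II eCRF captures all AEs whatever their grade and attribution.

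- **If it does:** state this in Section 10.2.2 or 12.4.1 and keep the all-cause tables.
- **If it does not:** in Sections 12.3 and 12.4.1, limit every pooled AE table and 90% Wilson interval to possible, probable or definite events of any grade plus all grade 3 and higher events. Show unrelated or unlikely grade 1-2 events for Phase I patients only, with the Phase I denominator.

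The cost is SAP or table-shell wording, with no new data collection. The downside of the second route is that there is no pooled all-cause grade 1-2 table, and the low-grade rates then depend on investigator attribution in an open-label, single-arm trial.

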### 10.3 Serious Adverse Events

#### 10.3.1 Definition

A serious adverse event (SAE) is any adverse event (experience) that in the opinion of either the investigator or sponsor results in **ANY** of the following:

- Death.
- A life-threatening adverse event (experience). Any AE that places a participant or participants, in the view of the Investigator or sponsor, at immediate risk of death from the reaction as it occurred. It does **NOT** include an AE that, had it occurred in a more severe form, might have caused death.
- Inpatient hospitalization or prolongation of existing hospitalization (for > 24 hours).
- A persistent or significant disability/incapacity or substantial disruption of the ability to conduct normal life functions.
- A congenital anomaly or birth defect.
- Important Medical Event (IME) that, based upon medical judgment, may jeopardize the participant and may require medical or surgical intervention to prevent one of the outcomes listed above.

Patients may be hospitalized for administrative or social reasons during the trial (e.g. days on which infusion takes place, long distance from home to site). These and other hospitalizations planned at the beginning of the trial do not need to be reported as an SAE.

#### 10.3.2 Reporting Serious Adverse Events

All new SAEs occurring from the date the participant signs the study consent until 30 days after the last intervention or a new treatment is started, whichever comes first, will be reported. The RPCI SAE Source Form is to be completed with all available information, including a brief narrative describing the SAE and any other relevant information.

SAEs occurring after the 30 day follow-up period that the investigator determines to be possibly, probably or definitely related to the study intervention should be reported.

SAEs identified as an Unanticipated Problem by the Investigator must be reported. Please refer to Section 10.6 for details on reporting Unanticipated Problems.

#### **10.4 Investigator Reporting: Notifying Boehringer Ingelheim (BI) and NCCN**

The principle investigator at each respective site will report all SAEs and non-serious AEs which are relevant to a reported SAEs and AESIs by fax using a MEDWATCH 3500A form with the completed BI FAX Cover Sheet to BI Unique Entry Point and NCCN, as detailed below in accordance with the following timelines:

- **Within 5 calendar days** upon receipt of initial and follow-up SAEs containing at least one fatal or immediately life-threatening event.
- **Within 10 calendar days** upon receipt of any other initial and follow-up SAEs.

Boehringer Ingelheim Pharmaceuticals, Inc.  
[name]  
[name]  
[contact]

**AND**

NCCN at

[[contact]](mailto:[contact])

Or

[contact]

For each adverse event, the investigator will provide the onset date, end date, intensity, treatment required, outcome, seriousness, and action taken with the investigational drug. The investigator will determine the relationship and expectedness with the investigational drug to all AEs as defined in the listed adverse event section of Boehringer Ingelheim's (BI's) Investigator Brochure for the Product.

The investigator does not need to actively monitor patients for adverse events once the clinical trial has ended. However, if the investigator becomes aware of an SAE(s) that occurred after the patient has completed the clinical trial (including any protocol specified follow-up period), it should be reported to BI if considered relevant by the investigator.

#### **10.5 Follow-Up for Serious Adverse Events**

All related SAEs should be followed to their resolution, until the study participant is lost to follow-up, the start of a new treatment, or until the study investigator assesses the event(s) as stable or irreversible. New information will be reported when it is received.

## 10.6 Unanticipated Problems

### 10.6.1 Definition

An Unanticipated Problem (UP) is any incident, experience, or outcome that meets all of the following criteria:

- Unexpected (in terms of nature, severity, or frequency) given:
  - a) The research procedures that are described in the study-related documents, including study deviations, as well as issues related to compromise of participant privacy or confidentiality of data.
  - b) The characteristics of the participant population being studied.
- Related or possibly related to participation in the research (possibly related means there is a reasonable possibility that the incident, experience, or outcome may have been caused by the procedures involved in the research).
- Suggests that the research places participants or others at a greater risk of harm (including physical, psychological, economic, or social harm) than was previously known or recognized and if in relation to an AE is also deemed **Serious** per **Section 10.3**.

### 10.6.2 Reporting Unanticipated Problems

Unanticipated problem reporting will begin at the time of participant consent. The Unanticipated Problem Form will be submitted to the CRS Compliance Office within 1 business day of becoming aware of the Unanticipated Problem.

When becoming aware of new information about an Unanticipated Problem, submit the updated information to CRS Compliance with an updated Unanticipated Problem Form. The site Investigator or designated research personnel will report all unanticipated problems, whether related or unrelated to the investigational agent(s) to the **IRB in accordance with their local institutional guidelines**.

## 10.7 FDA Reporting

When RPCI is the IND holder the following describes the FDA reporting requirements by timeline for AEs and new safety findings that meet the criteria outlined below:

### Within 7 Calendar Days

Any adverse event that meets **ALL** the following criteria:

- Related or possibly related to the use of the study drug;
- Unexpected; and
- Fatal or life-threatening.

**Within 15 Calendar Days**

Any adverse event that meets **ALL** the following criteria:

- Related or possibly related to the use of the study drug;
- Unexpected; and
- Serious but not fatal or life-threatening;

Or, meets **ANY** of the following criteria:

- A previous adverse event that is not initially deemed reportable but is later found to fit the criteria for reporting (report within 15 days from when event was deemed reportable).
- Any findings from other studies, including epidemiological studies, pooled analysis of multiple studies, or other clinical studies conducted with the study drug that suggest a significant risk in humans exposed to the drug.
- Any findings from animal or in vitro testing that suggest a significant risk for human participants including reports of mutagenicity, teratogenicity, or carcinogenicity or reports of significant organ toxicity at or near the expected human exposure.
- Any clinically important increase in the rate of occurrence of a serious, related or possibly related adverse event over that listed in the protocol or investigator brochure.

Sponsors are also required to identify in IND safety reports, all previous reports concerning similar adverse events and to analyze the significance of the current event in the light of the previous reports.

